5.4.5 Interim Analysis

N/A

5.4.6 Handling of Missing Data

We assume that the missing data will be missing at random. If the proportion of missing data is not more than 5%, we will ignore the missing data and perform complete case analyses. Otherwise, we will use multiple imputation to replace the missing data at follow-up for the primary cognitive outcome. Regardless of the proportion of missing data, we will constrain the voxelwise imaging analyses to complete cases because to our knowledge, there is no validated method to correct for missing data in such analyses.

6 Trial Administration

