The primary, secondary and exploratory outcomes as outlined in Aims 1 and 2 will also apply to Aim 3. All cognitive and functional MRI tasks will be repeated 12 weeks after the completion of the training program (Visit 4). These results will then be compared with those obtained at baseline and 6-week post-intervention using a 3x2 mixed ANOVA with an interaction term (dependent variables: cognitive test scores and functional connectivity and graph measures, between-subject factor: group, within-subject factor: time with three levels, i.e., baseline, 6-weeks post-intervention, and 12-weeks post-completion, interaction: group-by-time) ($p < 0.05$, two-tailed). A significant interaction will be followed by post hoc simple effects tests to determine the level(s) of interaction.

AIM 4: To explore the brain-cognition link associated with mental imagery training in PD

Exploratory Aim: We will examine the post-training brain-cognition relationship at the 6-week and 12-week timepoints in each group. We will test whether the post-training changes in task-specific whole-brain pairwise functional connectivity and graph measurements will predict the post-training differences in the Neuro-QoL Cognitive Function and composite executive test scores in each group.

Exploratory outcomes: This brain-behavior relationship at 6 weeks will be the exploratory outcome of Aim 2 and that at 12 weeks will be the exploratory outcome of Aim 3.

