5.4.2 Sample Size Considerations

We calculated the sample size based on the primary cognitive outcome, i.e., Neuro-QoL version 2 Cognitive Function scores. The Neuro-QoL Cognitive Function validation study with 120 PD patients who had mild disease (Hoehn & Yahr stage 2) showed mean \pm SD = 50.46 \pm

7.25.⁹⁷ A change of 2-6 T-scores have been considered a minimally important change in patient-reported outcome measures.¹⁰³

We estimated the sample size based on the assumption that there will be an average of 4 T-score improvement after mental imagery training using the G*Power 3.1 software^{104,105}. The repeated-measures ANOVA between-subject factor model with two groups and two measurements, with an effect size of $f=0.266$ (corresponding to a moderate effect size $d=0.53$), alpha 0.05, and power 0.80 yielded a total sample size of 86 (43 in each group). With an estimated 15% drop out ($86/0.85 \approx 101$) during the 6-week intervention period and another 15% drop out ($101/0.85 \approx 120$) in the subsequent 12-week period, we plan to recruit 120 subjects in total.

In our previous work with PD patients using motor (N=22) and visual (N=22) imagery training, we showed robust task-specific pairwise functional connectivity changes post-training especially in the respective motor and visual networks.⁴ Therefore, we think this sample size will also be adequate for the primary imaging outcome.

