To compare the task-specific whole-brain functional connectivity changes between the groups, we will perform pairwise functional connectivity analyses using the generalized psychophysiological interaction (gPPI) model. We will first convolve the 3-min task blocks in each mental imagery and video-watching run with the canonical hemodynamic response function. We will use the functionally defined cortical and subcortical nodes (N=268) of the whole-brain Shen atlas.⁵² For each subject, we will extract the average blood oxygenation level-dependent signal time courses calculated via the gPPI model from these nodes and correlate them with each other using Pearson correlations. The r values will correspond to the functional connectivity strength between node pairs. We will Fisher z-transform the r values and obtain group-level functional connectivity maps for statistical analyses.

Graph analysis

To compare the task-specific changes in local and global network properties between the groups, we will perform graph analyses on the pairwise functional connectivity data. Specifically, we will compute the 1) clustering coefficient, which shows the connectivity strength between neighboring nodes and is a measure of local network efficiency, and 2) betweenness centrality, which shows how well-connected a particular node is with all other nodes and is a measure of that node's potential as an integrative hub.¹⁰⁶ These graph measures will then be used in statistical analyses.

Sex as a biological variable

Sex differences in normal cognitive aging have been reported.¹⁰⁷ Reports on sex differences in PD-related cognitive decline have been variable. Sex differences in cognition in de novo PD patients have been found to be similar to those in normal aging.¹⁰⁸ On the other hand, male sex was found to be associated with PD-MCI,¹⁰⁹ and poorer performance in male vs female PD patients in executive functioning and processing speed have been demonstrated.¹¹⁰ In our study, both groups will be sex-matched and we will use sex as a covariate in separate analytical models to examine the potential sex-related differences in training response.

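### Section 5.4.6 restricts imaging to complete cases for a voxelwise reason that does not fit the planned node-pair and node-level outcomes; the cost falls mainly on the three-visit Aim 3 analysis.

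*Combined protocol and SAP*

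**What the plan says.** Section 5.4.6 sets out the missing-data rules in four steps.

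- The assumption: "We assume that the missing data will be missing at random".
- Small loss: "If the proportion of missing data is not more than 5%, we will ignore the missing data and perform complete case analyses".
- Larger loss: "we will use multiple imputation to replace the missing data at follow-up for the primary cognitive outcome".
- Imaging: "Regardless of the proportion of missing data, we will constrain the voxelwise imaging analyses to complete cases", the reason being that to the authors' knowledge "there is no validated method to correct for missing data in such analyses".

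Section 5.4.3 defines what the imaging analysis works on: "We will use the functionally defined cortical and subcortical nodes (N=268) of the whole-brain Shen atlas". Node time courses are correlated pair by pair and Fisher z-transformed. Clustering coefficient and betweenness centrality are then computed from the pairwise values.

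Section 5.4.1 tests these measures twice. Aim 2 uses a 2x2 mixed ANOVA on baseline and post-training scans. Aim 3 uses a 3x2 mixed ANOVA on all three visits ("dependent variables: cognitive test scores and functional connectivity and graph measures"). Section 5.4.2 expects 15% loss during the intervention and "another 15% drop out" in the following 12 weeks.

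**The concern.** The exemption rests on a property, being voxelwise, that none of the planned imaging outcomes has. Voxels appear only in acquisition (Section 5.1) and preprocessing (Section 5.4.3). Each outcome is a single number per subject per visit. A likelihood-based mixed model handles such a number with whatever visits are present, under the assumption that Section 5.4.6 already makes.

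There is also a literal reading. If the rule covers only voxelwise analyses, it covers nothing that is planned. Imputation is reserved for the primary cognitive outcome, so above 5% missing the imaging outcomes would then have no rule.

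At stake are precision and possible bias in Aim 3. A repeated-measures ANOVA on complete cases drops anyone without a T2 scan, together with that person's usable T0 and T1 scans. Sustained effect is the secondary objective (Section 3.3), but Section 4.2.1 also lists connectivity change across T2 among the primary imaging outcomes.

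**Working it through.** **Inputs.** From the documents: 120 subjects, 60 per arm (Section 4.3.1); 15% loss before T1 and a further 15% before T2 (Section 5.4.2); 268 nodes and two tasks (Section 5.4.3). Assumed: between-visit correlation r of 0.3 to 0.7 and unit variance at each visit, since the documents give neither.

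**The plan's own figures.** A between-factor repeated-measures ANOVA with f = 0.266, two measurements and an assumed correlation of 0.5 gives 86 subjects (power 0.804), as stated. 86/0.85 = 101.2 and 101/0.85 = 118.8. Rounding up at each step (86, 102, 120) gives the stated 120.

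**Number of outcomes.** 268 × 267/2 = 35,778 node pairs per task, or 71,556 over two tasks.

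**Scans available.** T1: 120 × 0.85 = 102. T2: 102 × 0.85 = 86.7, about 87. Missing: 15% at T1 and 1 − 0.85² = 27.75% at T2, both above the plan's 5% threshold.

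**Scans discarded.**
- Aim 3: acquired 120 + 102 + 87 = 309; used 3 × 87 = 261; discarded 48. These are 18 baselines of subjects lost before T1, plus 2 × 15 = 30 scans of subjects lost between T1 and T2.
- Aim 2: acquired 120 + 102 = 222; used 2 × 102 = 204; discarded 18, all baselines with no T1 scan.

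**Standard errors at r = 0.5, in SD units.** Per arm there are 60, 51 and 43.5 scans at T0, T1 and T2. Each expression is for the between-group difference in change.
- Aim 3, complete cases, either contrast: √(2 × (2 − 2r)/43.5) = √(2/43.5) = 0.214.
- T1 contrast, all scans: √(2 × [(1 − r²)/51 + (1 − r)²/60]) = √(2 × [0.75/51 + 0.25/60]) = 0.194, a reduction of 9.4%.
- T2 contrast, all scans, equal correlation between visits: √(2 × [(2/3)/43.5 + (1/9)(0.75)/51 + 0.25/60]) = 0.206, a reduction of about 4%.
- Aim 2, complete cases: √(2/51) = 0.198. All scans: 0.194 as above, a reduction of 1.9%.

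**Over the assumed range.** V is the variance ratio, complete cases to all scans. The reduction in SE is 1 − 1/√V.

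| r | T1 contrast, Aim 3 | T2 contrast, Aim 3 | Aim 2 |
|---|---|---|---|
| 0.3 | V = 1.237, 10.1% | V = 1.113, 5.2% | 2.7% |
| 0.5 | V = 1.218, 9.4% | V = 1.088, 4.1% | 1.9% |
| 0.7 | V = 1.199, 8.7% | V = 1.067, 3.2% | 1.1% |

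These closed forms treat the covariance as known. In simulation, with the covariance estimated, the T2 gain is somewhat smaller, hence about 2-5%. If correlation instead decays with time (AR(1)), the closed-form T2 ratios are 1.152, 1.138 and 1.119, or reductions of 6.8%, 6.3% and 5.5%.

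**Bias illustration.** Simulation with 60 per arm and 4,000 trials per setting. Dropout in one arm depends on the last observed value, with an assumed odds ratio of 2 to 3 per SD; dropout in the other arm is random. The complete-case T2 contrast is off by 0.03-0.10 SD over r = 0.3-0.7. At r = 0.5 it is off by 0.044 (odds ratio 2) and 0.067 (odds ratio 3). The sign depends on which values drop out. The likelihood estimate is near zero bias throughout.

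**The case against.** The strongest reply is that the main imaging test is hardly affected. Aim 2 is a separate two-visit analysis, so a missing T2 scan removes nobody from it, and the scans it loses are baselines without a follow-up. This stands. A reader might infer that the exemption undermines the T0-T1 imaging result; it does not, and the 9-10% gain belongs only to the T1 contrast inside the three-visit analysis.

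Second, the bias scenario is assumed. Nothing in the documents suggests that subjects leave because of a connectivity value. Section 5.3.2 reports no significant difference in dropout between groups in the previous imagery study. Dependence of that strength could not hold for every one of 35,778 pairs. Even at r = 0.5 the bias is 0.044/0.215 = 0.20 to 0.067/0.215 = 0.31 of the complete-case standard error. If loss depends on mood, cognition or adherence, a model with only group, visit and their interaction would not remove that bias. All of this stands. It limits the claim to possible bias.

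Third, complete-case analysis is itself a stated rule, Section 5.4.3 commits all fMRI analysis steps to CONN, and mass fitting outside it may raise convergence and small-sample degrees-of-freedom problems. A Gaussian model may also suit a skewed measure such as betweenness centrality poorly. These are fair practical grounds, but Section 5.4.6 does not give them. They call for checks and for keeping the CONN result, and do not rescue the stated reason.

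**Conclusion.** The point holds, mainly for Aim 3. The reason in Section 5.4.6 does not fit the outcomes in Section 5.4.3. On complete cases the three-visit analysis would discard about 48 of 309 scans. Using them would lower the standard error by about 9-10% (T1 contrast) and 2-5% (T2 contrast). For Aim 2 the gain is 1-3%.

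These sizes rest on the plan's dropout, assumed correlations of 0.3-0.7 that are equal between visits, and monotone loss. Scans rejected for motion would add to the loss.

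Two stronger readings are not supported. The documents do not show that the imaging results will be biased: 0.03-0.10 SD is an illustration under odds ratios that the documents give no evidence for. Nor do they leave imaging without any rule on the natural reading; the rule is complete cases, with a justification that does not apply. Whether a validated method exists for truly voxelwise analyses cannot be judged from the documents and does not matter here.

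**What to change.** 1. In Section 5.4.6, replace the reference to voxelwise analyses with the node-pair and node-level analyses actually planned.
2. For Aim 3, analyse each Fisher z and each graph measure on all available scans with a likelihood-based mixed model: group, visit, group-by-visit, and correlated visits within subject. Apply the FDR correction to the interaction p-values.
3. Check the distribution of the graph measures, betweenness centrality in particular, and transform where skewed. State how non-converging fits are handled.
4. Report the complete-case CONN result for Aim 3 beside the mixed-model result.
5. Aim 2 may stay in CONN on T0-T1 complete cases, with the all-available-scans model as a sensitivity analysis. State that completeness is judged on those two visits only.

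The cost is SAP wording, export of values from CONN, and about 71,556 pairwise model fits outside it. At a timed 0.05 s per fit, that is 71,556 × 0.05 = 3,578 s, about one hour, plus the graph measures and the checks. The downside is leaving the CONN second-level workflow for Aim 3. No new patients, visits or scans are needed.

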6.1 Ethical Considerations: Informed Consent/Accent and HIPAA Authorization

Possible Deception

There is no possibility for deception.

Payment

Subjects will be compensated for their participation and for travel expenses (e.g., parking, cab ride). The in-person visits are lengthy and training sessions require daily time commitment. Therefore, we think it is important to reimburse subjects for their time.

Each in-person visit \$100 (x4)
 Each completed training week \$50 (x4)
 Total for parking \$50

Discovery of Previous Unknown Conditions

If a worrisome finding is seen on the subjects imaging scan, a radiologist or another physician will be asked to review the relevant images. Based on his or her recommendation (if any), the principal investigator or consulting physician will contact the subject, inform the subject of the finding, and recommend that they seek medical advice as a precautionary measure.

Permanent Medical Records

No information will be added to the subject's permanent medical records.

Consent

Consent forms will be Yale IRB-approved and the participant will be asked to read and review the document. A member of the research team authorized to obtain consent will explain the research study to the participant and answer any questions that may arise. This conversation will take place in a private environment via Zoom.

Participants will have the opportunity to carefully review the written consent form and ask questions prior to signing. The participants will have the opportunity to discuss the study with their family or surrogates, or think about it prior to agreeing to participate. The participant will sign the informed consent document prior to any procedures being done specifically for the study. Participants will be informed that participation is voluntary and that they may withdraw from the study at any time, without prejudice. A copy of the informed consent document will be given to the participants for their records.

The purpose, research procedures, any risk that these procedures might entail, and any possible benefits will be discussed in detail in language appropriate for the individual's level of understanding. Subjects will be encouraged to ask questions and given enough time to discuss any aspect of the study with the research team. Subsequently, they will have to demonstrate understanding of the study procedures and what is expected of them. Once subjects understand the study, they will be asked if they wish to participate. If they do, they will be asked to electronically sign the consent form at the Zoom video-call screening visit.

Evaluation of Subject's Capacity to Provide Consent

Capacity will be assessed directly in the course of attempting to obtain informed consent. When the member of the research team authorized to obtain consent has reviewed the study, they will ask the subject to explain the major elements of the study. Those elements are a) this is a research study (not routine treatment), b) participation is voluntary, c) study procedures, d) risks, e) benefits. Open-ended questions such as "Can you tell me the main things that you would do in this study? Can you tell me the main risks of the study?" will be used to assess understanding and appreciation of the facts. Subject will then be expected to make a rational choice: "Considering the risks and benefits we have discussed, would you like to take part in this study?" Based on the subject's responses the team member will make a final judgment about capacity for consent. If the subject has capacity and agrees to the study, they will sign the consent form.

Subject Coercion

The voluntary nature of the study will be stressed and reiterated throughout conversations with potential participant during the consent process. It will be made clear that the individual's refusal to participate will in no way affect the care which they are entitled to.

Sensitive Data and Privacy

Hard copies of HIPAA identifiers, consent forms, clinical screening information, and MRI screening form will be kept in a locked filing cabinet.

Study data will not contain personally identifiable information and will be labeled using a coding system. The data labels will contain the subject code, date and time of recording, and mode and condition of recording. Only the principal investigator, [name], will have access to the centrally and electronically stored and password-protected subject identification list to decode data files.

De-identified data will be stored on username- and password-protected servers provided by the Yale University and managed by the Yale IT Department.

Upon completion of the study, study binders will be stored in a locked facility for the amount of time required by law. After this time, the study binders will be destroyed by shredding. The electronic databases will stay on the password-protected research computers until the study closes. The link to personal information will be kept until the end of the study, after which time the link will be destroyed and the data will become anonymous. The data will be kept in this anonymous form indefinitely.

6.2 Institutional Review Board (IRB) Review

This will be a phase 1 randomized clinical trial.

Modifications and Updates

The protocol will be submitted to the IRB for review and approval. No research activity will commence until IRB approval received. Any change to the protocol or study team will require an approved IRB amendment before implementation. The IRB will determine whether informed consent and HIPAA authorization are required.

A study closure report will be submitted to the IRB after all research activities have been completed.

Unanticipated Problems

Unanticipated Problems Involving Risks to Subjects or Others (UPIRSOs), including adverse events, are not anticipated. In the unlikely event that such events occur, they will be reported in accordance with federal and Yale University IRB rules.

Reportable Events (which are events that are serious or life-threatening and unanticipated (or anticipated but occurring with a greater frequency than expected) and possibly, probably, or definitely related) or UPIRSOs that may require a temporary or permanent interruption of study activities will be reported immediately, followed by a written report within 5 calendar days of [name] becoming aware of the event to the IRB and any appropriate funding and regulatory agencies (using the UPIRSO Reporting Form 710 FR 4). Serious or unexpected adverse events that are not life-threatening will also be reported immediately followed by a written report within 5 calendar days of [name] becoming aware of the event to the IRB and any appropriate funding and regulatory agencies. Expected or non-serious adverse events will be reported at the time of continuing review. For each adverse event, [name] will record the onset, end, intensity, required treatment, outcome, seriousness, and action taken.

[name] will apprise study personnel of all UPIRSOs and adverse events that occur during the conduct of this research project through regular study meetings.

6.3 Subject Confidentiality

Participant confidentiality and privacy is strictly held in trust by the participating investigators, their staff, and the sponsor(s) and their interventions. Therefore, the study protocol, documentation, data, and all other information generated will be held in strict

confidence. No information concerning the study or the data will be released to any unauthorized third party.

All research activities will be conducted in as private a setting as possible.

The representatives of the Yale IRB or regulatory agencies may inspect all documents and records required to be maintained by the investigator.

The study participant's contact information will be securely stored for internal use during the study. At the end of the study, all records will continue to be kept in a secure location for as long a period as dictated by the Yale IRB and Institutional policies.

Study participant research data, which is for purposes of statistical analysis and scientific reporting, will be transmitted to and stored on username- and password-protected servers provided by the Yale University and managed by the Yale IT Department in [name] lab. This will not include the participant's contact or identifying information. Rather, individual participants and their research data will be identified by a unique study identification number. The study data entry and study management systems used will be secured and password protected. At the end of the study, all study databases will be de-identified and archived in [name] lab.

Access

Only the principal investigator, [name], will have access to the centrally and electronically stored and password-protected subject identification list to decode data files. Principal investigator and research staff will have access to study data to perform statistical analyses and to monitor fidelity of the data.

Recorded Identifiers

The following information for research will be collected and recorded for each subject:

- HIPAA identifiers: Name, date of birth, sex, phone, email, postal address. Postal address will be used to mail the debit card in a nondescript envelope to subjects for study payments.
- Clinical screening information: Handedness; any history or current condition of alcohol/substance use, neurological or psychiatric disorders such as brain tumor, stroke, central nervous system infection, multiple sclerosis, movement disorder (other than PD), seizures, dementia, depression, bipolar disorder, schizophrenia, attention deficit disorder, obsessive compulsive disorder; and history of head injury with loss of consciousness.
- The Yale MRRC MRI Safety Questionnaire will be used for MRI screening.

Storage and Security

Risk for potential breach of confidentiality will be minimized by the use of non-identifying labeling and the secure storage of electronic and paper files. All team members will use encrypted research computers.

Hard copies of HIPAA identifiers, consent forms, clinical screening information, and MRI screening form will be kept in a locked filing cabinet in [name] lab.

De-identified paper records will be kept in binders in [name] lab.

Data on paper records will also be entered in electronic databases and stored on secure Yale servers (Yale REDCap).

Imaging data will be transferred securely to workstations for analysis and stored on HIPAA-compliant secure central storage servers ("Storage@Yale") provided by the Yale IT Department for a monthly fee.

